6.9.5 Vital Signs

Vital signs (blood pressure, heart rate) will use the average of the triplicate assessments collected at each timepoint. If the average is derived in the eCRF, then that average will be used for analysis. If a triplicate is collected but the average is not determined in the eCRF, then the average of available values will be derived and used for analysis.

The change from baseline will be calculated as: *the visit value minus the baseline value*, for the following vital sign parameters:

- Systolic blood pressure (SBP; mmHg)
- Diastolic blood pressure (DBP; mmHg)
- Heart rate (beats/minute)
- Respiratory rate (breaths/minute)

- Body temperature (Celsius [C])
- Weight (kg)

Maintenance Period records will also display changes from Titration Period Baseline.

CS values, as collected on the CRF, will be summarized and separately flagged in a listing.

6.9.6 Physical Examination

Physical examination results will be listed.

6.9.7 Local Tolerability

Local tolerability will be assessed using the Modified Draize Scale and Injection Site Discomfort questionnaires following protocol-specified timepoint following SC injections of XP-8121. The Modified Draize Scale assesses Erythema and Edema on a 0 to 4 point scale with 0 being None and 4 being Severe.

Injection site discomfort will be assessed using an 11-point Numeric Rating Scale (NRS) and an Injection Site Discomfort Description and Duration Questionnaire following injection of XP-8121. Injection Site Discomfort Intensity will be categorized into the following groups: Mild = 1 – 3, Moderate = 4 – 6, and Severe = 7 – 10.

Time until onset of discomfort (minutes) and Duration of discomfort (minutes) will be summarized as reported on the eCRF.

7. ANALYSIS SETS

Analysis Set	Definition	Used for Analyses
Safety Population	All subjects who received at least one dose of XP-8121.	Disposition, Demographics, Medical History, Disease History, Concomitant Medications, Deviations, Safety Analyses, Tolerability endpoints Secondary endpoints, Exploratory endpoints (except PK related endpoints)
Completer Population	All subjects who completed the Maintenance Period and exhibit normalized TSH throughout the Maintenance Period while on a stable dose for approximately 6 weeks. Subjects with a reduced dose at any point during the Maintenance Period will not be included.	Dose Conversion Factor analysis, Sensitivity analysis of Change from Baseline of Blood Thyroid Hormone Concentrations Secondary Endpoint
PK Population	All safety population subjects who participated in the PK sub-study, who do not have any major protocol deviations affecting the PK endpoints and for whom a sufficient number of samples is available to determine at least one PK parameter.	PK analyses

8. STATISTICAL METHODS

8.1 General Methodology

Unless otherwise specified, statistical analyses will be 2-tailed and assessed at the 5% significance level.

Tabulations will be produced for all measured data. For categorical variables, summary tabulations of the number and percentage of subjects within each category (with a category for missing data) of each measure will be presented. For continuous variables, the number of subjects (n), mean, standard deviation (SD), median, minimum, and maximum will be presented. Geometric means and coefficient of variation (%CV) may be presented for certain analyses.

Subject listings of all data from the case report forms (CRFs) and any derived variables will be presented.

8.2 Adjustments for Covariates

Not applicable.

8.3 Handling of Dropouts or Missing Data

Drop-out subjects will not be replaced.

In general, there will be no replacement of missing data points. All data recorded on the eCRF for enrolled subjects will be included in data listings that will accompany the clinical study report.

When considering AE and Concomitant Medications, partial start/end dates will be managed in a conservative fashion so that if there is any possibility that the available partial information could reasonably result in the AE being treatment-emergent or the medication being concomitant, then it will be imputed as such. Specifically:

- If the start day is missing but month and year are present:
 - o If the known month/year are the same as the month/year of the first dose of treatment, then impute to the date of the first dose of treatment;
 - o Otherwise, impute the day to 01.
- If the start day and month are both missing but the start year is present:
 - o If the known year is the same as the year of the first dose of treatment, then impute to the date of the first dose of treatment;
 - o Otherwise, impute the day and month to 01January.
- If the start date is completely missing, impute to the date of the first dose of treatment, unless the end date suggests it could have started prior to this, in which case impute to 01January of the same year as the end date.
- When imputing a start date, ensure that the new imputed date is on or prior to the end date of the AE or medication.
- If the end date is missing or partial, and the AE/medication is not ongoing, then impute the missing/partial end date as follows:
 - o If the end day is missing but month and year are present:

- If the known month/year are the same as the month/year of the first dose of treatment, then impute to the date of the first dose of treatment;
 - Otherwise, impute the day to the last day of the month.
 - If the end day and month are both missing but the end year is present:
 - If the known year is the same as the year of the first dose of treatment, then impute to the date of the first dose of treatment;
 - Otherwise, impute the day and month to 31December.
 - If the end date is completely missing, impute to the date of the first dose of treatment.
 - When imputing an end date, ensure that the new imputed date is on or after the start date of the AE or medication.
- Other unexpected combinations of partial date information (e.g., known month but missing day and year) will be managed as needed on a case-by-case basis.

If samples are collected below the limit of quantification or using “<xx”, then use the “xx” value divided by 2 for analysis.

The handling of missing data will be discussed throughout sections 6 and 9 of the SAP, as applicable.

8.4 Multi-Center Studies and Pooling of Centers

Not Applicable.

8.5 Multiple Comparisons/Multiplicity

Not Applicable.

8.6 Interim Analyses and Data Monitoring Committees

Not Applicable.

8.7 Examination of Subgroups

Additional subgroup analysis may be performed at the discretion of the sponsor. Details are described in [Section 9.9](#).

9. STATISTICAL ANALYSIS

9.1 Subject Disposition and Analysis Sets

Analysis sets will be summarized by subject counts and percentages.

Subjects screened and screen failures (with reasons) and those who enroll, complete, or discontinue early (with reasons) will be summarized with subject counts and percentages. Subject disposition information per the eCRF will be listed. A by-subject listing of those who discontinue early will include dates of treatment start and end, informed consent, study end, and discontinuation reason.

9.2 Protocol Deviations

Subjects with at least one major protocol deviation will be summarized with counts and percentages within deviation category, sub-category, and deviation type.

9.3 Demographics and Baseline Characteristics

Demographic and other baseline characteristics will be summarized.

Descriptive statistics (n, mean, SD, median, minimum, and maximum) will be summarized for age (years), baseline height (cm), baseline weight (kg), and baseline BMI (kg/m^2). The number and percentage of subjects will be summarized for sex, race, ethnicity, hypothyroidism history type, and prior oral levothyroxine dose.

The number and percentage of subjects with at least one medical history event will be summarized within SOC and PT categories. Subjects will be counted only once within each SOC and PT.

9.4 Prior and Concomitant Therapies

The number and percentage of subjects with at least one prior medication will be summarized using WHO ATC Level 2 class and preferred names. Subjects will be counted only once within each ATC class and standardized (generic) medication name. Concomitant medications will be summarized likewise.

9.5 Analysis of Primary Endpoints

The final dose conversion factor will be assessed by comparing the ln-transformed final XP-8121 SC dose (in μg) that maintained normalized TSH throughout the Maintenance Period to the ln-transformed daily oral levothyroxine dose (in μg) each subject was taking before the study, using a linear mixed effects model with treatment (i.e., XP-8121 or oral levothyroxine) as fixed effects, and subject as random effect. A Variance Components (diagonal) covariance matrix will be used. If the model does not converge, then the compound symmetric covariance matrix will be used and defined in a footnote.

Geometric Least Square Means (LSM) by treatment, geometric mean ratios of XP-8121 SC dose vs daily PO levothyroxine dose (i.e. the final dose conversion factor), and the 90% CIs for the final dose conversion factor will be presented for the completer population with primary hypothyroidism.

Individual dose conversion factor, calculated as final XP-8121 SC dose (in μg) divided by prior oral levothyroxine dose (in μg), will also be listed. A line plot will display the final dose conversion factor versus the prior oral levothyroxine dose.

In addition, a scatterplot will be provided with relative day of dose on the x-axis and individual dose conversion factor on the y-axis. Data will be grouped into all subjects in Titration Period, subjects who completed the Maintenance Period with a stable dose and normalized TSH, and all other subjects in Maintenance Period.

Sensitivity analyses will be performed using the same analyses methods defined above but with other analysis populations, if applicable. No plots will be created for sensitivity analyses. Populations used in sensitivity analyses are as follows (the analysis for subjects with any hypothyroidism diagnosis will only be performed if not all subjects had primary hypothyroidism) :

- Subjects with primary hypothyroidism who maintained normal TSH throughout Maintenance Period (allowing for dosing changes during Maintenance Period)
- Subjects with primary hypothyroidism who maintained both normal TSH and fT4 throughout Maintenance Period (allowing for dosing changes during Maintenance Period)
- Subjects with any hypothyroidism diagnosis who maintained normal TSH throughout Maintenance Period (allowing for dosing changes during Maintenance Period)
- Subjects with any hypothyroidism diagnosis who maintained both normal TSH and fT4 throughout Maintenance Period (allowing for dosing changes during Maintenance Period)
- Completer population with primary hypothyroidism who also maintained normal fT4 throughout Maintenance Period
- Completer population with any hypothyroidism diagnosis
- Completer population with any hypothyroidism diagnosis who also maintained normal fT4 throughout Maintenance Period

Analyses of safety endpoints include incidence, frequency, severity, and relationship to study drug or TEAEs. CS vital sign measurements, safety laboratory test results, ECGs, and physical examination findings will be listed and qualitatively analyzed where applicable.

Analyses of the tolerability assessments Modified Draize Scale and Injection Site Discomfort questionnaires are described in [Section 9.8.7](#).

9.6 Analysis of Secondary Endpoints

Secondary endpoints will be analyzed as follows (only subjects with primary hypothyroidism will be considered for the secondary endpoints):

Endpoint	Applicable to	Timespan	Analysis Method
Normalized Values	TSH	Throughout the Maintenance Period/ End of Maintenance Period	The number and percentage of subjects with normal values will be presented along with the number of subjects entering the Maintenance Period. Corresponding 95% CIs will be included using the Clopper-Pearson method. Values will be presented with the denominator comprising subjects entering the Maintenance Period and subjects in the safety population.

Endpoint	Applicable to	Timespan	Analysis Method
Observed Values that are lower than, within, or higher than the normal range	T4 fT4 TSH	During the Titration and Maintenance Periods)	
The number and percentage of subjects with results will be summarized by three categories based on the normal range: "Low", "Normal", or "High".
 
A boxplot will be included with the x-axis displaying the starting dose of XP-8121 and the y-axis showing fT4 following the first dose of XP-8121 on the y-axis.

9.7 Analysis of Exploratory Endpoints

Exploratory Endpoints will be summarized as follows (only subjects with primary hypothyroidism will be considered for the non-PK exploratory endpoints):

Endpoint	Applicable to	Timespan	Analysis Method
Observed Values	T4 fT4 TSH	Titration Period Maintenance Period	
Summarized by each protocol-specified timepoint using descriptive statistics (n, mean, SD, median, minimum, and maximum).
 
A line plot of the mean observed value will be provided over duration of the study.
 
A spaghetti plot with each subject compiled will be provided over the duration of the study for fT4 and TSH.
 
Repeat analysis using the Completer Population

Endpoint	Applicable to	Timespan	Analysis Method
Change from Baseline	T4 fT4 TSH	Titration Period Maintenance Period	
Summarized by each protocol-specified timepoint using descriptive statistics (n, mean, SD, median, minimum, and maximum).
 
A line plot of the mean change from baseline will be provided for each period.
 
Repeat analysis using the Completer Population

Total Plasma Concentrations	T4 T3	168-hr PK Period for Subjects in PK sub-study	
Summarized by collection timepoint and period using descriptive statistics (N, mean, SD, SD, %CV, median, minimum, maximum, geometric mean, and geometric %CV).
 
A line plot with mean and SD of concentrations by timepoint will be provided along with a by subject plot of concentration by timepoint.

t_{max} (hours)	T4 T3	168-hr PK Period for Subjects in PK sub-study	Summarized using descriptive statistics (n, mean, SD, %CV, median, minimum, maximum, geometric mean, and geometric %CV).
C_{max} (ng/mL)	T4 T3	168-hr PK Period for Subjects in PK sub-study	Summarized using descriptive statistics (n, mean, SD, %CV, median, minimum, maximum, geometric mean, and geometric %CV).
$AUC_{0-168hrs}$	T4 T3	168-hr PK Period for Subjects in PK sub-study	Summarized using descriptive statistics (n, mean, SD, %CV, median, minimum, maximum, geometric mean, and geometric %CV).
Minimum Concentration (C_{min}) (ng/mL)	T4 T3	168-hr PK Period for Subjects in PK sub-study	Summarized using descriptive statistics (n, mean, SD, %CV, median, minimum, maximum, geometric mean, and geometric %CV).

Endpoint	Applicable to	Timespan	Analysis Method
Last concentration (C _{trough}) (ng/mL)	T4 T3	168-hr PK Period for Subjects in PK sub-study	Summarized using descriptive statistics (n, mean, SD, %CV, median, minimum, maximum, geometric mean, and geometric %CV).
Mean concentration at steady state (C _{ss})	T4 T3	168-hr PK Period for Subjects in PK sub-study	Summarized using descriptive statistics (n, mean, SD, %CV, median, minimum, maximum, geometric mean, and geometric %CV).
Observed Values	Convenience Domain Score of the TSQM-9	Per collection timepoint	
Summarized by each protocol-specified timepoint using descriptive statistics (n, mean, SD, median, minimum, and maximum).
 
The analysis of TSQM-9 will be hierarchically analyzed to ensure control of the family-wise type I error rate at the 0.05 level, with the Convenience Score first, Overall Satisfaction score second, and Effectiveness third.
 
Hypothesis tests for the three domain scores are:
 
H₀: No difference between oral levothyroxine and once-weekly XP-8121 SC treatments
 
H₁: Difference between oral levothyroxine and once-weekly XP-8121 SC treatments.
 
Each domain score will be compared between the two treatments (XP-8121 and Oral Levothyroxine) using a paired t-test at each timepoint.
 
A line plot will be provided with the mean of Oral Levothyroxine as a reference line and the mean 95% Confidence Interval XP-8121 results at each collection point.

Endpoint	Applicable to	Timespan	Analysis Method
Observed Values	Overall Satisfaction Domain Score of TSQM-9	Per collection timepoint	
Summarized by each protocol-specified timepoint using descriptive statistics (n, mean, SD, median, minimum, and maximum). A p-value from a paired t-test at each timepoint will be displayed per note above for Convenience score.
 
A line plot will be provided with the mean of Oral Levothyroxine as a reference line and the mean 95% Confidence Interval XP-8121 results at each collection point.

Observed Values	Effectiveness Domain Score of TSQM-9	Per collection timepoint	
Summarized by each protocol-specified timepoint using descriptive statistics (n, mean, SD, median, minimum, and maximum). A p-value from a paired t-test at each timepoint will be displayed per note above for Convenience score.
 
A line plot will be provided with the mean of Oral Levothyroxine as a reference line and the mean 95% Confidence Interval XP-8121 results at each collection point.

Observed Values	Subject Preference Survey	Per collection timepoint	The subject counts and percentages for each answer to each question will be summarized.

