#### 13.5.3.1. Analysis of Exploratory Endpoints

All exploratory endpoints except for PK endpoints will be analyzed for the safety population, for subjects with primary hypothyroidism only and for all subjects, if applicable. TSH, total and free T4 measures and changes from baseline will be summarized by each protocol-specified timepoint using descriptive statistics. Analysis of PK endpoints will be described in Section 13.6.

The analysis of the exploratory endpoint of TSQM-9 domain scores will be gated on results from the primary endpoint analysis. The three domain scores will be hierarchically analyzed to ensure control of the family-wise type I error rate at the 0.05 level, with the Convenience score first, Overall Satisfaction score second, and Effectiveness third. Hypothesis tests for the three domain scores will be based on null hypotheses that assume no difference between oral levothyroxine and once-weekly XP-8121 SC treatments. Each domain score will be compared between the two treatments using a paired t-test.

Subject counts and percentages for each answer to each question from the Subject Preference Survey will also be presented.

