**If you had the choice between these two medications for thyroid replacement therapy, which one would you choose?**

- a. once-daily oral pill
- b. once-weekly injection
- c. no preference

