**If you prefer one of the administration methods, how strong is the preference?**

- a. Very strong
- b. Fairly strong
- c. Slightly strong
- d. Not very strong

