**If you prefer one of the administration methods, what are the main reason(s) for your preference? Choose all that apply.**

- a. Convenience
- b. Ease of administration
- c. Frequency of administration
- d. My level of compliance with therapy
- e. Confidence in my therapy
- f. Other

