Observed Values	Convenience Domain Score of the Treatment Satisfaction Questionnaire for Medication (TSQM-9)	Per collection timepoint	
Convenience Score is the transformed total of items 4, 5, and 6 as follows:
 
If all items are non-missing: $([\{\text{Sum of Item 4 to Item 6}\} - 3] \text{ divided by } 18) * 100$.
 
If one item is missing: $([\{\text{Sum of non-missing items 4, 5, and 6}\} - 2] \text{ divided by } 12) * 100$.
 
If two or more items are missing, then do not calculate.

Endpoint	Applicable to	Timespan	Derivation
Observed Values	Overall Satisfaction Domain Score of TSQM-9	Per collection timepoint	
Overall Satisfaction is the total of Item 7, 8, and 9.
 
If all items are non-missing: $([\{ \text{Sum of Item 7 to Item 9} \} - 3] \text{ divided by } 14) * 100$.
 
If item 7 or 8 is missing: $([\{ \text{Sum of non-missing Item 7 to Item 9} \} - 2] \text{ divided by } 10) * 100$.
 
If item 9 is missing: $([\{ \text{Sum of item 7 and item 8} \} - 2] \text{ divided by } 8) * 100$
 
If two or more items are missing, then do not calculate.

Observed Values	Effectiveness Domain Score of TSQM-9	Per collection timepoint	
Effectiveness is the total of Items 1, 2, and 3.
 
If all items are non-missing: $([\{ \text{Sum of Item 1 to Item 3} \} - 3] \text{ divided by } 18) * 100$.
 
If one item is missing: $([\{ \text{Sum of non-missing Item 1 to Item 3} \} - 2] \text{ divided by } 12) * 100$.
 
If two or more items are missing, then do not calculate.

Observed Values	Subject Preference Survey	Per collection timepoint	N/A

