9.9 Subgroup Analyses

If a sufficient number of subjects with secondary or tertiary hypothyroidism are included in the study, additional analyses for the secondary efficacy endpoints and non-PK exploratory endpoints may be performed on all subjects regardless of hypothyroidism diagnosis at the discretion of the sponsor.

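### Preference Survey questions 2 and 3 (strength and reasons) are not planned by preferred treatment, so as written their percentages carry no direction

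*SAP*

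**What the plan says.** The survey in Protocol Appendix D has three questions.

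- Question 1 sets the direction: "If you had the choice between these two medications for thyroid replacement therapy, which one would you choose". The answers are the daily pill, the weekly injection or no preference.
- Question 2 asks for strength on a four-point scale: "If you prefer one of the administration methods, how strong is the preference".
- Question 3 asks for reasons: "If you prefer one of the administration methods, what are the main reason(s) for your preference? Choose all that apply". The options (convenience, ease, frequency, compliance, confidence, other) do not name a treatment.

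The planned analysis is one sentence in each document. SAP 9.7 states: "The subject counts and percentages for each answer to each question will be summarized". Protocol 13.5.3.1 states: "Subject counts and percentages for each answer to each question from the Subject Preference Survey will also be presented". The endpoint table in SAP 6.8 defines no derived variable; its entry reads "Subject Preference Survey Per collection timepoint N/A".

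The general rule for categorical data in SAP 8.1 is that "summary tabulations of the number and percentage of subjects within each category (with a category for missing data) of each measure will be presented". It does not mention questions that apply only to some respondents. The one subgroup provision, SAP 9.9, concerns disease type: further analyses "may be performed on all subjects regardless of hypothyroidism diagnosis at the discretion of the sponsor". Nothing provides for a split by preferred treatment.

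**The concern.** Question 1 is the only item that carries direction. A subject who very strongly prefers the pill and one who very strongly prefers the injection give the same answer to question 2. Convenience or confidence in therapy can likewise be a reason for choosing either product in question 3. If each question is tabulated alone, both groups fall into the same cells, and the percentages describe the strength of, and reasons for, some preference without saying which.

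Subjects with no preference raise a second gap. Questions 2 and 3 do not apply to them, but the plan does not say whether they stay in the denominator, are dropped from it or appear in the missing category.

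At stake is whether two of the three items of a named exploratory endpoint can be interpreted. A mixture of directions cannot be ruled out in advance. The survey is also given at the Early Termination Visit (Protocol 11.4), and SAP section 7 uses the Safety Population for the non-PK exploratory endpoints, so subjects who stopped early are not excluded on that ground.

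**Working it through.** **Plan's own figure.** There is none to reproduce. The documents give no expected answers, sample size or power for the survey. All counts below are assumptions, apart from the ceiling of about 44 enrolled subjects (Protocol 7.2). Even 44 is an upper bound on respondents, because SAP 9.7 restricts the non-PK exploratory endpoints to primary hypothyroidism.

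**Step 1: questions against analysis.** Question 1 names the treatments, so counts per answer are complete. Questions 2 and 3 are conditional on having a preference in either direction and name no treatment, so counts per answer lose the direction. Neither analysis sentence adds a cross-tabulation or a denominator.

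**Step 2: what a pooled percentage can tell the reader.** Let N_I and N_P be the numbers preferring the injection and the pill. Let S be the number in both groups together who report a strong preference (very or fairly strong).

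- Pooled percentage = S / (N_I + N_P).
- Given S, the strong count among injection-preferrers lies between max(0, S − N_P) and min(N_I, S).
- Among pill-preferrers it lies between max(0, S − N_I) and min(N_P, S).

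Assume 40 subjects have a preference and S = 24, so the pooled figure is 24/40 = 60%.

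| Assumed split (injection/pill) | Strong among injection-preferrers | Strong among pill-preferrers |
|---|---|---|
| 20/20 | 4/20 to 20/20 = 20% to 100% | 4/20 to 20/20 = 20% to 100% |
| 28/12 | 12/28 to 24/28 = 43% to 86% | 0/12 to 12/12 = 0% to 100% |
| 34/6 | 18/34 to 24/34 = 53% to 71% | 0/6 to 6/6 = 0% to 100% |
| 38/2 | 22/38 to 24/38 = 58% to 63% | 0/2 to 2/2 = 0% to 100% |
| 40/0 | 24/40 = 60% exactly | none |

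At 28/12 the two extremes are opposite findings: 24/28 (86%) strong for the injection with 0/12 for the pill, or 12/28 (43%) with 12/12 (100%). Both give the same pooled 24/40. The question 1 table would show the 28/12 split but could not tell the two cases apart.

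**Step 3: denominator.** Add 4 assumed subjects with no preference. The same 24 answers are 24/40 = 60% of those with a preference, or 24/44 = 55% of all respondents. The plan does not say which is meant.

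**Step 4: question 3.** The same bounds apply to each reason taken alone, since each is a yes/no count within the two groups.

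**The case against.** The strongest reply is that the SAP is silent on layout and has not decided to pool. A table of questions 2 and 3 by the question 1 answer would still meet the sentence in SAP 9.7, and the table shells are in a separate document that is not available here (SAP section 13). This stands in part: the final output may already be split. But nothing in either document tells the programmer to do so or which denominator to use.

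The second reply is that little depends on it. The endpoint is a descriptive summary with no hypothesis or test. SAP 8.1 also plans listings of all case report form data, so with at most about 44 respondents the three answers can be linked by hand. This stands, and it limits the point to a minor one.

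The third reply is that the illustrations use invented answers. That also stands: if nearly all preferences go one way, the pooled figure is close to that group's own.

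A reader might infer more than the documents support:

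- **That the whole survey is uninformative about the treatments.** Question 1 asks for the choice directly, and its planned percentages are sound.
- **That the objective of comparing satisfaction is undermined.** That comparison rests mainly on the TSQM-9 domain scores, which have their own paired tests and testing order.
- **That no-preference subjects will be counted as missing.** SAP 8.1 adds a missing category, but the coding of a skipped conditional question is not stated.
- **That the results will be presented as reasons for preferring XP-8121.** Neither document labels them so, and the questions are neutral in wording.

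**Conclusion.** The point holds for questions 2 and 3 only. The plan as written yields percentages without direction and with no stated denominator. They approximate a treatment-specific figure only when nearly all preferences go one way. Under the assumed pooled 60%, the uncertainty about injection-preferrers runs from 43% to 86% at a 28/12 split and narrows to 58% to 63% at 38/2. The actual size depends on answers that the documents do not predict and on shells that are not available. No error rate, power, or primary or secondary conclusion is touched, and the data remain recoverable from the listings. This is a minor point, worth making because the better table costs almost nothing.

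**What to change.** In SAP 9.7, add to the Subject Preference Survey row that questions 2 and 3 will be tabulated by the question 1 answer (pill or injection), with the number of subjects choosing that treatment as denominator. State that subjects with no preference will be shown as not applicable rather than missing. Leave question 1 as planned, and check that the table shell agrees.

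The cost is a short addition to the SAP and one table shell. No new data, no change to the questionnaire and no further test are needed.
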